9.1.3. Pharmacogenomic Analysis

Details of pharmacogenomic data collection and analysis will be included in a SAP addendum, appendix or separate SAPs.

10. STATISTICAL SOFTWARE

All derived datasets, data listings, summaries, and statistical programming/analyses will be performed using SAS® 9.4 or higher.

12. APPENDIX

12.1. Efficacy Variables Calculation Methods

12.1.1. Unified Huntington's Disease Rating Scale – Total Functional Capacity (UHDRS-TFC)

The UHDRS-TFC is the standard and well-accepted clinical scale for staging and tracking the progression of HD using functional capacity. Scores range from 0 to 13, with 13 as the least affected and 0 as complete incapacity. The scale assesses the participant's capacity to undertake domestic chores (0=Unable to 2=Normal), activities of daily living (0=Total Care to 3=Normal), take care of finances (0=Unable to 3=Normal), maintain care level (0=Full time skilled nursing to 2=Home), and maintain their occupation (0=Unable to 3=Normal). UHDRS-TFC questionnaires are collected as specified in the SoA ([Table 1](#) and [Table 2](#)) to assess change from Baseline.

A UHDRS-TFC evaluation will only be considered valid if all 5 assessments of Domestic Chores, Activities of Daily Living, Finances, Care Level, and Occupation are completed. If any of these is not completed, the UHDRS-TFC assessment will be considered invalid and treated as missing value.

Participants with improvement or no worsening in UHDRS-TFC at a particular post-baseline visit during Main Study are defined as those with change from Baseline ≥ 0 at that visit.

TFC responders at a scheduled visit during OLE are defined as participants with change from Main Study Baseline in UHDRS-TFC ≥ -1 .

12.1.2. Unified Huntington's Disease Rating Scale – Total Motor Score (UHDRS-TMS)

The UHDRS-TMS is the sum of 31 individual motor ratings from the 15 items of the UHDRS, with each assessment rated on a 5-point scale from 0 (normal) to 4 (maximally abnormal). Higher scores indicate more severe motor impairment. The worst possible score is 124. UHDRS-TMS questionnaires are collected to assess change from Baseline.

The subscales of UHDRS-TMS include:

- Gait and balance score, defined as the sum of UHDRS Items 13, 14 and 15 (gait, tandem walking, and retropulsion pull test)
- Eye movement score, defined as the sum of UHDRS Items 1a Horizontal, 1b Vertical, 2a Horizontal, 2b Vertical, 3a Horizontal, 3b Vertical (ocular pursuit, saccade initiation, and saccade velocity)
- Dystonia score, defined as the sum of Items 11a – 11e
- Chorea score, defined as the sum of Items 12a – 12g

Participants with improvement or no worsening in UHDRS-TMS at a particular post-baseline visit during Main Study are defined as those with change from Baseline ≤ 0 at that visit.

[figure not shown]
12.1.3. Unified Huntington's Disease Rating Scale – Composite Score (cUHDRS)

The cUHDRS ([Schobel et. al., 2017](#)) is a composite measure of motor, cognitive, and global functional decline computed as follows:

$$cUHDRS = \left[\left(\frac{TFC - 10.4}{1.9} \right) - \left(\frac{TMS - 29.7}{14.9} \right) \right. \\ \left. + \left(\frac{SDMT - 28.4}{11.3} \right) + \left(\frac{SWR - 66.1}{20.1} \right) \right] + 10$$

A cUHDRS responder is defined as one with change from Baseline in cUHDRS ≥ 1 .

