
 To evaluate the effect of pridopidine on functional capacity, motor function, cognition, and other measures of efficacy over time in participants with HD 	
 Proportion of participants with improvement or no worsening (change from Baseline \geq 0 point) at Week 65 in UHDRS-TFC Change from Baseline to Week 52 in UHDRS-TFC score Change from Baseline to Week 78 in UHDRS-TFC score Change from Baseline to Week 65 in Quantitative motor (Q-Motor) [REDACTED] [REDACTED] Change from Baseline to Week 65 in UHDRS Total Motor Score (TMS) Change from Baseline to Week 65 in Symbol Digit Modalities Test (SDMT) Change from Baseline to Week 52 in UHDRS-TMS score Proportion of participants with improvement or no worsening in

	Clinical Global Impression of Change (CGI-C) at Week 65
Non-multiplicity Adjusted Secondary Endpoints	

 • To evaluate the effects of pridopidine in participants with HD 	
 • Change from Baseline to Week 26 and 39 in the UHDRS-TFC • Proportion of participants with improvement or no worsening in UHDRS-TFC (change from Baseline ≥ 0) at Weeks 26, 39, 52 and 78 • Change from Baseline to Weeks 26, 39, 52 and 78 in cUHDRS • Proportion of participants with change from Baseline ≥ -1 in cUHDRS at Weeks 26, 39, 52, 65 and 78 • Change from Baseline to Week 26, 39 and 78 in the UHDRS-TMS score • Proportion of participants with improvement or no worsening in UHDRS-TMS (change from Baseline ≤ 0) at Weeks 26, 39, 52, 65 and 78 • Change from Baseline to Weeks 26, 39, 52, 65 and 78 in: 
 – UHDRS-TFC Scale sub-items (capacity to undertake domestic chores, activities of daily living, capacity to manage finances, care level and occupation) – UHDRS-TMS sub-scores for: 
 ○ Gait and balance score (defined as the sum of UHDRS-TMS domains gait, tandem walking, and retropulsion pull test) ○ Eye movement ○ Dystonia • Change from Baseline to Weeks 26, 39, 52 and 78 in SDMT • Change from Baseline to Weeks 26, 39, 52, 65 and 78 in Stroop Word Reading (SWR)

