3.2. Primary, Secondary and Other Efficacy Endpoints and Safety Endpoints

The study endpoints are based on the study objectives listed in the protocol Section 3 and are listed below.

The endpoints described here as the component of the estimand, “variable (or endpoint)” in Section A.3.3 “Estimand Attributes” of ICH E9 R(1)², reflect how efficacy is measured for each participant using different assessments (e.g., UHDRS-TFC), timepoints (e.g., Week 65) and methods (e.g., change from Baseline, being a responder). The detailed calculation or derivation for these endpoints is included in Appendix Section 12.1.

In order to preserve Type I error, the multiplicity-adjusted secondary efficacy endpoints will be tested in sequential order as indicated in Section 3.2.2.

In SAP v1.0, it was stated that the combined in-clinic and virtual assessments may be used to define UHDRS-TFC related endpoints in the presence of missing values due to the pandemic impact of COVID-19. As of September 2022, <2% of all scheduled in-clinic visits from all participants were not performed or had UHDRS-TFC assessments missing. Since the proportion of missing in-clinic visits or assessments is very small, and the UHDRS-TFC virtual assessments have not been previously validated, together with the heterogeneity that may exist due to the time interval (6 to 7 weeks) between in-clinic and virtual assessments, the UHDRS-TFC-related endpoints will be defined using in-clinic visits only. Exploratory analysis will be performed by using virtual UHDRS-TFC assessments for primary endpoint (details in Section 7.3).

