3.2.3. Non-multiplicity Adjusted Secondary Efficacy Endpoints

The non-multiplicity adjusted secondary efficacy endpoints (listed in Section 2) will evaluate the efficacy of pridopidine 45 mg bid vs. placebo, as measured by change from Baseline to post-baseline scheduled visits in UHDRS-TFC (total score and subscales), cUHDRS, UHDRS-TMS (total score and subscales), dystonia score for those participants with severe dystonia at Baseline (defined as UHDRS-TMS-dystonia score ≥ 4), SDMT, SWR, Q-Motor measurements [REDACTED] at Weeks [REDACTED]

26, 39, 52, 65 and 78, if not presented as primary or multiplicity-adjusted secondary endpoints.

The proportion of participants with response in cUHDRS, UHDRS-TMS, Q-Motor [REDACTED] [REDACTED], and CGI-C at Weeks 26, 39 (not for Q-Motor assessments), 52, 65 and 78, if not presented as primary and multiplicity-adjusted secondary endpoints, will also be evaluated as non-multiplicity adjusted secondary efficacy endpoints. The response in each endpoint is defined as follows:

- Improvement or no worsening in Q-Motor [REDACTED] with change from Baseline ≤ 0 at corresponding post-baseline visit
- Improvement or no worsening in UHDRS-TMS with change from Baseline ≤ 0 at corresponding post-baseline visits
- Change from Baseline in cUHDRS ≥ -1 at corresponding post-baseline visits
- Response in CGI-C defined using different thresholds (i.e., 1, 1 to 2, 1 to 3, 1 to 4) at corresponding post-baseline visits

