7.4.3. Other Multiplicity Adjusted Secondary Efficacy Variable and Analysis

For continuous endpoints such as change from Baseline using observed data only, the main estimand will be similar to the non-EMA-Estimand for the primary endpoint, analyzed using the mITT population with treatment policy strategy to handle ICEs. An MMRM model as described in Section 7.2 for the primary endpoint will be used with Baseline value of the analyzed variable replacing Baseline UHDRS-TFC as a covariate. For the specified visits, the LSMs, SE of the estimates, p-values, and 2-sided 95% CIs will be provided for the within treatment group changes from Baseline and for the comparison of change from Baseline between pridopidine and placebo.

Supportive estimands for continuous endpoints will be similar to the EMA-Estimand for the primary endpoint, with population as the ITT population and missing values imputed using copy reference method under MNAR assumption. Additional missing value imputation approach under MAR assumption may be used as a sensitivity analysis.

For analysis of change from Baseline in UHDRS-TFC at Week 78, main analysis will include observed values at scheduled visits up to 78 weeks. A sensitivity analysis for Week 78 endpoints will be performed with assessments between Week 65 and 78 mapped to Week 78.

For positive response defined using values of continuous variables:

- Unless otherwise specified, where a decrease reflects disease progression, a responder will be defined as those with no change or improvement (change from Baseline ≥ 0)
- Unless otherwise specified, where an increase in score reflects disease progression, a responder will be defined as those with change from Baseline ≤ 0

Main estimands for binary endpoints will be similar to the main estimand for the binary UHDRS-TFC response, analyzed in the mITT population and with ICEs handled by a combined composite and hypothetical strategy. Supportive estimand for the binary endpoints will be similar to Supportive Estimand 1 for the binary UHDRS-TFC response. All responder analyses or analyses of binary variables will be performed using logistic regression as indicated for the binary secondary variable above in Section 7.4.1.

The p-values from the main estimand will be used in the hierarchical testing for multiplicity adjusted secondary endpoints following the order described in Section 3.2.2.

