7.6. Other Exploratory Efficacy Variable and Analyses

Other exploratory efficacy variables include:

- Change from Baseline to Weeks 26, 52, 65 and 78 in PBA-s domains subscale scores and total scores
- Change from Baseline to Weeks 26, 52, 65 and 78 in HDQoL

These will be analyzed similar as described in Section 7.5 for non-multiplicity adjusted secondary efficacy variables in their main estimand.

Responder analyses for select efficacy endpoints, such as UHDRS-TFC and cUHDRS, using clinically meaningful thresholds may be performed.

In addition, the observed virtual UHDRS-TFC assessments at virtual Baseline, Weeks 13, 32, and 58 and change from virtual Baseline (Day -7 Visit) at each post-baseline virtual visit will be summarized.

The impact of PIN_{HD}, defined as prognostic index normed for HD, on treatment effects for select efficacy variables may be explored using categorized PIN_{HD} score, where PIN_{HD} = (PI_{HD} - 883) / 1044, and PI_{HD} = 51 × TMS + (-34) × SDMT + 7 × Age × (CAG - 34), defined as prognostic index for HD (10).

Treatment effect on change from Baseline in weight over visits may also be explored adjusting for sex and age.

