7.7. OLE Efficacy Analyses

The final analyses of OLE data will be performed at the End of OLE when all participants complete the OLE EoS visit. Interim analyses may be performed as needed.

The OLE analysis will be presented using the following labels for treatment group, in the order displayed:

- Placebo bid (Main Study) to Pridopidine 45 mg bid (OLE)
- Pridopidine 45 mg bid (Main Study) to Pridopidine 45 mg bid (OLE)
- Total of above two groups (where applicable)

Proportion of participants with change of UHDRS-TFC from Main Study Baseline ≥ -1 by treatment group and the difference between treatment groups at each OLE visit will be provided along with a 2-sided 95% CIs using normal approximation and p-values from a logistic regression similar to that described in Section 7.4.1. This analysis will be repeated using a threshold of 0 for proportion of participants with change of UHDRS-TFC from Main Study Baseline ≥ 0 .

Summary statistics will be presented for UHDRS-TFC, cUHDRS, UHDRS-TMS, Q-Motor

[REDACTED] and Q-Motor [REDACTED]

[REDACTED] by treatment group and visit during the OLE period as described below:

- Change from Main Study Baseline and the observed values of UHDRS-TFC, cUHDRS, UHDRS-TMS, and Q-Motor measurements at each OLE visit
- Change from OLE Baseline and the observed values of UHDRS-TFC, cUHDRS, UHDRS-TMS, and Q-Motor measurements at each OLE visit

In addition, the durability of treatment response to pridopidine in the OLE period will be assessed by the proportion of participants who continue to respond to pridopidine in OLE among the responders in double-blind treatment period. Responders defined using following endpoints will be assessed for the durability:

- Change from Main Study Baseline to Week 65 in UHDRS-TFC ≥ 0 , and change from Main Study Baseline to each OLE visit in UHDRS-TFC ≥ -1
- Change from Main Study Baseline to Week 65 in UHDRS-TFC ≥ 0 , and change from Main Study Baseline to each OLE visit in UHDRS-TFC or ≥ 0
- Change from Main Study Baseline to Week 65 in cUHDRS ≥ -1 , and change from Main Study Baseline to each OLE visit in cUHDRS ≥ -1.5

- Change from Main Study Baseline ≤ 0 in UHDRS-TMS at Week 65, and change from Main Study Baseline ≤ 0 in UHDRS-TMS at each OLE visit
- Change from Main Study Baseline ≤ 0 in Q-Motor [REDACTED] and change from Main Study Baseline ≤ 0 insec in Q-Motor [REDACTED] at each OLE visit

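### SAP Appendix 12.1.3 sets the cUHDRS responder cut-off at ≥ 1, but every other statement of this endpoint in the protocol and SAP sets it at ≥ -1

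*SAP*

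**What the plan says.** Appendix 12.1.3 of the SAP gives the cUHDRS formula and then one responder rule: "A cUHDRS responder is defined as one with change from Baseline in cUHDRS ≥ 1". It names no visit, study period or particular analysis.

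The endpoint itself is listed in the Protocol 1.1 synopsis as: "Proportion of participants with change from Baseline ≥ -1 in cUHDRS at Weeks 26, 39, 52, 65 and 78". Protocol 3.1.1 and SAP 2 list it in the same terms. SAP 3.2.3, in a list presented as the definition of response for each endpoint, has: "Change from Baseline in cUHDRS ≥ -1 at corresponding post-baseline visits". The open-label durability analysis in SAP 7.7 identifies double-blind responders by: "Change from Main Study Baseline to Week 65 in cUHDRS ≥ -1".

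The endpoint section and the appendix are linked explicitly in SAP 3.2: "The detailed calculation or derivation for these endpoints is included in Appendix Section 12.1".

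**The concern.** Two parts of the same SAP each claim to define cUHDRS response, and their cut-offs have opposite signs. Under ≥ -1 the endpoint counts participants who improved, stayed stable or declined by no more than one point. Under ≥ 1 it counts only those who improved by at least one point. These are different clinical questions.

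The SAP says that it prevails over the protocol, but that does not settle the matter because the conflict is inside the SAP. No rule ranks the body of the SAP above its appendix.

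If the analysis were programmed from 12.1.3 as written, the reported proportions at Weeks 26, 39, 52, 65 and 78 would not be those of the endpoint listed in either document. If the conflict is still open at unblinding, it could also be asked whether the cut-off was chosen after the data were seen.

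**Working it through.** **Cut-offs side by side**

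| Place | Cut-off for change from Baseline |
|---|---|
| Protocol 1.1 | ≥ -1 |
| Protocol 3.1.1 | ≥ -1 |
| SAP 2 | ≥ -1 |
| SAP 3.2.3 | ≥ -1 |
| SAP 7.7 (at Week 65) | ≥ -1 |
| SAP 12.1.3 | ≥ 1 |

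**Direction of the score.** The divisors come from the 12.1.3 formula. The centring constants and the added 10 cancel when a change is taken:

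change in cUHDRS = ΔTFC/1.9 − ΔTMS/14.9 + ΔSDMT/11.3 + ΔSWR/20.1

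TFC, SDMT and SWR enter positively and are better when higher. TMS enters negatively and is worse when higher. A higher cUHDRS is therefore better, and ≥ 1 means improvement.

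**Who changes class.** Components not named are held unchanged.

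| Case | Change in cUHDRS | At ≥ -1 | At ≥ 1 |
|---|---|---|---|
| No change | 0 | responder | non-responder |
| TFC +1 | 1/1.9 = +0.53 | responder | non-responder |
| TFC -1 | -1/1.9 = -0.53 | responder | non-responder |
| TFC -1, TMS +5 | -0.526 − 5/14.9 = -0.526 − 0.336 = -0.86 | responder | non-responder |
| TFC +2 | 2/1.9 = +1.05 | responder | responder |
| TFC -2 | -2/1.9 = -1.05 | non-responder | non-responder |

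In general, the two rules disagree for every change in [-1, +1) and agree everywhere else.

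**Illustrative size.** The documents give no mean or SD of cUHDRS change, so the following rests on assumption only. Suppose the change is normal with mean between 0 and -1.5 and SD between 1 and 2. Over the grid of means 0, -0.5, -1 and -1.5 and SDs 1, 1.5 and 2, the responder share runs from about 31% to 84% at ≥ -1 and from about 1% to 31% at ≥ 1. At mean -0.5 and SD 1.5 it is 63% against 16%. The share classified differently runs from 0.401 − 0.106 = 0.295 (mean -1.5, SD 2) to 0.841 − 0.159 = 0.682 (mean 0, SD 1).

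**Could +1 belong to another analysis?** The appendix labels its TFC responder rules by period; for the extension it reads: "TFC responders at a scheduled visit during OLE are defined as participants with change from Main Study Baseline in UHDRS-TFC ≥ -1". The cUHDRS line carries no such label. In the extension, SAP 7.7 uses ≥ -1 at Week 65 and ≥ -1.5 at the extension visits, so +1 fits neither period. Where the appendix intends several cut-offs, as for CGI-C in 12.1.5.2, it lists them.

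**The case against.** The strongest objection is that everything turns on one character, and the text was read from PDF. Hyphens have been lost elsewhere: the repeated header of SAP Table 1 appears both with and without the hyphen in its double-blind label. A lost minus sign in 12.1.3 is therefore possible. Against this, the minus sign is intact in all five other cUHDRS statements and in the TFC rule in 12.1.1 of the same appendix. This point stands as a reason to check the source first. It does not remove the discrepancy in the text as available.

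Second, +1 could be intended as an extra threshold. SAP 7.6 allows this in general terms: "Responder analyses for select efficacy endpoints, such as UHDRS-TFC and cUHDRS, using clinically meaningful thresholds may be performed". SAP 7.5 and Protocol 9.4.3 also allow other thresholds. All of these are optional and none names +1, whereas 12.1.3 is worded as the definition. The reading cannot be ruled out, and if it is correct the line needs a label.

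Third, a programmer with five consistent statements in view may never follow the sixth. That lowers the practical risk. However, SAP 3.2 names the appendix as the place for derivations.

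Finally, the default in SAP 7.4.3 might seem relevant: "where a decrease reflects disease progression, a responder will be defined as those with no change or improvement (change from Baseline ≥ 0". It shows that +1 is out of pattern, since no change counts as response there. It does not identify the right sign. It applies only unless otherwise specified, it sits in the section on multiplicity-adjusted endpoints, and ≥ -1 departs from it too. The conclusion does not rely on it.

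**Conclusion.** The inconsistency holds. As written, SAP 12.1.3 gives a decision threshold that conflicts with Protocol 1.1 and 3.1.1 and with SAP 2, 3.2.3 and 7.7, and nothing in the documents resolves it. The weight of the text favours ≥ -1, and a missing minus sign, in the SAP itself or lost in PDF reading, is the likely cause.

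The consequence is limited to one non-multiplicity-adjusted secondary endpoint, analysed at five visits. The primary endpoint, the key secondary endpoint (mean change in cUHDRS), the testing order, the sample size and the durability rule that SAP 7.7 states for itself do not depend on this line. The classification result needs only the 12.1.3 formula. The share of participants affected would need a distribution that the documents do not give. Confidence is medium because the source PDF has not been checked. This is a point to consider, not a threat to the trial's main conclusions.

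**What to change.** Check the source PDF of SAP 12.1.3. If the minus sign is printed there, nothing needs changing. If it is absent, either change the cut-off to ≥ -1 so that it agrees with SAP 3.2.3, or keep +1 and label it explicitly as an additional exploratory threshold, with ≥ -1 given as the endpoint definition.

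SAP 5 requires changes before database lock and unblinding to be recorded in an addendum, and later ones to be described in the CSR. SAP version 3.0 is dated 28 March 2023 and the protocol expected the Main Study to run until Q1 2023, so the sponsor should confirm which route applies. The cost is one line of text, with no effect on data collection, the test hierarchy or the sample size. The program for this endpoint should be checked against the agreed cut-off.

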12.1.4. Quantitative Motor (Q-Motor)

12.1.5. Clinical Global Impression

12.1.5.1. Modified Clinical Global Impression of Severity (modified CGI-S)

The CGI-S (modified) scale was initially designed to assess treatment response in participants with mental disorders but is now used widely in a range of illnesses. Illness severity is rated by qualified site personnel on a 7-point scale (1 = normal, not at all ill to 7 = among the most extremely ill participants) as shown in the table below. The assessment is based on qualified site personnel judgment, supported by a comprehensive, semi structured, participant/caregiver interview.

CGI-S (modified) will be collected at Baseline.

Description	Score
Normal, not at all ill	1
Borderline ill	2
Mildly ill	3
Moderately ill	4
Markedly ill	5
Severely ill	6
Extremely ill	7

12.1.5.2. Clinical Global Impression – Change (CGI-C)

The CGI-C scale measures the change in the participant's clinical status from a specific point in time, using a 7-point scale, ranging from 1 (very much improved) to 7 (very much worse), with a score of 4 indicating no change.

Responder analyses will be performed at Week 65 as a secondary efficacy endpoint with analysis at all other post-baseline visits as additional efficacy analyses. Responder analyses comparing participants randomized to pridopidine vs placebo will be performed using CGI-C for those:

- (a) who have no change or improve (Scores of 1,2,3 or 4)
- (b) who Minimally or more improved (Scores of 1,2, or 3)
- (c) who Are Much or Very Much improved (Scores of 1 or 2)
- (d) who are Very Much improved (Score of 1)

Description	Score
Not assessed	0
Very Much Improved	1
Much Improved	2
Minimally improved	3
No change	4
Minimally worse	5
Much worse	6
Very much worse	7

12.1.6. Exploratory Assessments

12.1.6.1. Stroop Word Reading (SWR)

The SWR is a neuropsychological test commonly used to measure the participant's attention and mental flexibility. The participant's accuracy and speed at the SWR will be recorded and used to track the progression of cognitive deterioration. Scores reflect the number of correct responses in 45 seconds. Higher scores indicate better performance.

SWR is collected to assess the proportion of responders and change from Baseline for efficacy endpoints.

